**Parenting Now (PN).** REAL Prevention LLC (RP) adapted the Parent Handbook to digital format, Parenting Now (PN), and established its feasibility for a broader audience through a successful Phase I SBIR to address these limitations. In Phase II, our team will refine and complete PN based on our Phase I findings examining parents' preferences. These refinements include: 1) PN will have core modules that cover essential topics (e.g., why it is important for parents to talk with their students, improving communication, parent permissiveness toward adolescent drinking, how alcohol works in the body, and the difficulty of making

accurate judgments of impairment); 2) Customization, user-initiated tailoring, is accomplished through offering a menu of optional topics that parents can choose to acquire content specific to their interests (e.g., other commonly used substances that adolescents combine with alcohol use, parents' drinking and drug history, and the importance of being committed to a healthy lifestyle); and 3) Personalization, system-initiated tailoring, is accomplished through adapting content to the parent's communication style, based on the work of RP's [name]. Sundar's work demonstrates that both customization and personalization can improve engagement with digital materials, but that they work differently for different people. All the refinements are based on the findings of Phase I research and add to the innovation of the PN. We now seek to complete the PN adaptation, test its efficacy in a randomized control trial (RCT), and prepare it for rapid and widespread national and international dissemination via collaboration with D.A.R.E. America and other channels.

**Aim 1.** Toward this extent, Specific Aim 1 will conduct a RCT to evaluate PN's effects on youth alcohol use and other substance use assessed at 3 waves (baseline, 1 mo., and 6 mo.) using a rigorous study design that includes a nationally-representative sample and an active control condition.

**H1:** Students in the PN condition will engage in less alcohol use and consequences (primary outcome) than in the control condition.

**H2:** Students in the PN condition will engage in less marijuana use, nicotine use, and their combined use with alcohol (secondary outcome) than in the control condition.

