As noted above, teens who complete their consent will be routed to an online survey. After the baseline assessment, parents will be randomized equally to 1 of 2 groups. Parents in the treatment condition will receive a link to KB’s secure server to access PN and complete a brief question set assessing their parent communication style. Parents in the control condition will receive a link to that server to access publicly available SAMHSA alcohol prevention materials for parents. Both conditions take the same length of time to navigate. Parents in both conditions will be instructed to access the materials and discuss the information with their teens during the next month. Thus, the proposed research will have a strong active control condition for which to examine differences in effects increasing the rigor of the study. The link to the website will contain instructions on how to register and use the site. Parents who do not register with the website will receive reminders every 5 days for three weeks; after three weeks, study staff will contact parents by telephone and encourage them to register. RP staff will provide technical assistance if parents have problems using the website. In our previous studies, we have had parental compliance rates with web surveys, parenting materials

from the Parent Handbook, parent-ratings of the Parent Handbook and so on, that have reliably exceeded 88%. We anticipate no problems regarding use of the PN in the proposed research.

Teen participants in both the treatment and control groups will receive a follow-up survey (~15 minutes to complete) at 1 and 6 months post-baseline, which will allow us to examine any changes in the proposed mediator variables. Parents randomized to the PN condition will complete a brief question set at the beginning of the PN intervention that assesses parenting communication style and allows for personalization. Parents also receive an immediate posttest to measure fidelity and reactions to PN. Baseline, 1- and 6-month follow-up surveys will each take approximately 25-30 minutes to complete.

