**Table 2. Measures Reflective of Theoretical Model in Figure 1**

Construct	Target	Time	alpha
Primary Outcomes			
Alcohol Use (Daily Drinking, HED, Quantity/Frequency, Peak) 	Teen	T1-T3	>.70-.90
Alcohol-related Consequences (e.g., Riding with a drunk driver) 	Teen	T1-T3	>.75-.85
Secondary Outcomes			
Marijuana Use 	Teen	T1-T3	>.70-.90
Nicotine Use (e.g., Cigarette Use; E-cigarette Use; Smokeless Tobacco) 	Teen	T1-T3	>.70-.90
Combined Substance Use	Teen	T1-T3	>.70
Tertiary Outcomes (Mediators)			
Parent Communication 	Parent,Teen	T2	>.75
Alcohol Motives/Expectancies/Willingness/Norms 	Teen	T2	>.70 - >.85
Moderators			
Background Demographics (Birth Sex, Gender Identity, Sexual Orientation, Age, Race / Ethnicity)	Teen	T1	–

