4.3. Outcome Measures

Type	Name	Time Frame	Brief Description
Primary	Alcohol Use	Project years 1-2	A standard drink definition will be provided: a standard drink consists of 12 oz. beer or wine cooler, 8.5 oz. of malt liquor, 4 oz. of wine, 3.5 oz. fortified wine, or 1.5 oz. of hard liquor. Typical weekly drinking: participants will respond to the Daily Drinking Questionnaire(DDQ; Collins et al., 1985) to indicate number of drinks consumed on each day of a typical week within the past six months. Participants will report maximum number of drinks consumed on an occasion within the past month and number of hours spent drinking on that occasion using the Quantity/Frequency/Peak questionnaire (QFP; Dimeff et al., 1999; Marlatt et al., 1998). Drunkenness will be assessed by asking how many times in the past month participants have gotten drunk, or very high from alcohol using a 6-point scale: (0) never to (5) 9 or more. Heavy episodic drinking will be measured for females and males separately, asking for number of times they've had 4/5, respectively, drinks in a row within two hours.
Secondary	Marijuana Use	Project years 1-2	Frequency of use will be assessed by asking how often participants used marijuana during the past six months using a 7-point scale ranging from (0) never to (6) 40 or more times.
Secondary	Combined Use	Project years 1-2	Frequency of combined use will be assessed for participants indicating marijuana and nicotine use with a single item: During times you used marijuana, how often did you also drink alcohol? using a 6-point scale ranging from (0) never to (5) 40 or more times. For participants that indicate their peak drinking occasion a follow up question will assess whether marijuana or nicotine was also used(yes or no).
Secondary	Consequences of Alcohol Use	Project years 1-3	Alcohol-related consequences (e.g., said or done embarrassing things, blackout) from the past six months will be measured using the established Brief Young Adult Alcohol Consequences Questionnaire (BYAACQ; Read, Kahler, Strong, & Colder, 2006). Response options will again be measured on the same a 7-point scale above.
Secondary	Nicotine Use	Project years 1-2	Frequency of use will be assessed by asking how often participants used nicotine products (tobacco, vaping, snuff) during the past six months using a 7-point scale ranging from (0) never to (6) 40 or more times.

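### Combined use with alcohol: no frequency item covers nicotine with alcohol, the filter does not match the item it governs, and the scoring of skipped items is unstated

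*Combined protocol and SAP*

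**What the plan says.** - **Hypothesis.** H2 (Significance, Aim 1) reads: "Students in the PN condition will engage in less marijuana use, nicotine use, and their combined use with alcohol". Specific Aim 1 and the Aim 1 analysis under Data Analysis name the same secondary outcomes.
- **First item.** Section 4.3, Combined Use: "Frequency of combined use will be assessed for participants indicating marijuana and nicotine use with a single item". The question is: "During times you used marijuana, how often did you also drink alcohol", on a 0 to 5 scale where 0 is never.
- **Second item.** Same row: "For participants that indicate their peak drinking occasion a follow up question will assess whether marijuana or nicotine was also used(yes or no".
- **Timing.** Table 2 lists "Combined Substance Use" as a teen measure at T1 to T3. Randomization comes between T1 and T2: "After the baseline assessment, parents will be randomized equally to 1 of 2 groups".
- **Population.** Substance use is not needed for entry (Participant Recruitment and Procedures). The Aim 1 analysis is to be intent-to-treat and to include everyone randomized.
- **Not stated.** The plan does not say what score a teen receives when the frequency item is skipped, or how the frequency item and the yes/no item form one outcome. Missing Data and Attrition analyses discuss FIML, multiple imputation and dropout, but not items skipped by design.

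**The concern.** A secondary hypothesis about two substances with alcohol has a frequency measure for only one of them. For nicotine with alcohol, the data would be a yes on a single occasion that could equally mean marijuana. A null or positive result on combined use could not be assigned to nicotine.

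The filter adds a second problem. At T2 and T3, whether the question is asked depends on the teen's own marijuana and nicotine use, which PN is meant to change. If skipped responses became missing or excluded, the arms would be compared among teens selected after randomization. That comparison would lose the protection of randomization and would conflict with the intent-to-treat statement.

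The outcome is not peripheral: the Dissemination Plan devotes one of three main papers to co-occurring use. Questions that were never asked cannot be recovered after data collection.

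**Working it through.** **1. Coverage of H2 by the items in Section 4.3**

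| Component of H2 | Frequency item | Peak-occasion item |
|---|---|---|
| Marijuana with alcohol | Yes, filtered | Pooled with nicotine |
| Nicotine with alcohol | None | Pooled with marijuana |

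**2. The filter under its two readings**

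- Read as both substances: a teen who combines alcohol and marijuana but does not use nicotine is skipped, although the question is about that teen's behaviour.
- Read as either substance: a nicotine-only user is asked about times of marijuana use that did not occur.

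Neither reading matches the item.

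**3. When the filter depends on treatment**

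At T1 it precedes randomization and does no harm. Section 4.3 asks about marijuana and nicotine over the past six months. If those answers drive the filter, the T2 window reaches back about 6 - 1 = 5 months before baseline, so it is only partly post-randomization. The T3 window falls almost wholly after randomization.

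**4. The plan's power figure, reproduced**

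Inputs: power above 0.80 for 5% to 10% of outcome variance with about 200 per arm (Statistical Design and Power); 320 and 280 dyads expected at 1 and 6 months (Participant retention). Alpha is not stated; two-sided 0.05 is assumed. For a two-group comparison, f² = r²/(1 - r²), noncentrality = f² × N, and F has 1 and N - 2 degrees of freedom.

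At r² = 0.05, f² = 0.05/0.95 = 0.0526.

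- N = 400: power 0.996
- N = 320: power 0.98
- N = 280: power 0.97

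At r² = 0.10, power is about 1.00 for all three. The stated figure reproduces when every teen has a score.

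**5. The same formula if only filtered users were compared at 6 months**

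The share passing the filter is an assumption, so a range is shown.

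| Assumed share | N = 280 × share | Power, r² = 0.05 | Power, r² = 0.10 |
|---|---|---|---|
| 5% | 14 | 0.12 | 0.21 |
| 10% | 28 | 0.22 | 0.40 |
| 20% | 56 | 0.39 | 0.69 |
| 30% | 84 | 0.55 | 0.86 |

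Power of 0.80 needs 152 users at 5% of variance (152/280 = 54%) or 73 at 10% (73/280 = 26%). These rows hold the share of variance fixed. They do not say that one absolute effect is easier to detect once many zeros are added.

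**6. Direction of bias, with hypothetical numbers**

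Suppose 20% of controls use marijuana, half with a co-use score of 1 and half with 4. Suppose PN stops half of the light users.

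- Users only: control (0.10 × 1 + 0.10 × 4)/0.20 = 2.5; PN (0.05 × 1 + 0.10 × 4)/0.15 = 3.0.
- All teens, non-users 0: control 0.50; PN 0.05 × 1 + 0.10 × 4 = 0.45.

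The users-only contrast points to harm, while the all-teen contrast points to benefit.

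**The case against.** Several stronger readings are tempting, and the documents do not support them.

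- **That combined use is asked only of marijuana and nicotine users, and only about marijuana.** The peak-occasion item goes to teens who report a peak drinking occasion, whatever their drug use, and it names nicotine. Nicotine with alcohol is thinly measured, not absent.
- **That the H2 comparison rests on a subset formed after randomization.** Filtering a question is not the same as restricting an analysis. A non-user's co-use is logically zero, the scale has a zero, and the Aim 1 text promises to include everyone randomized. What stands is that the score for a skipped item is unstated.
- **That the subset can be sized from the 22.7% past-month drinking rate quoted for ages 16 to 17.** The frequency item is not filtered on drinking, the recall windows differ, and no marijuana, nicotine or co-use rate is given.

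It is also fair to say that Section 4.3 gives brief descriptions. The questionnaire, cited as Appendix B, is not part of the document and may hold fuller skip logic. H2 could also be read as one pooled construct, since Table 2 has a single row; separate estimates are a reasonable reading but not an explicit requirement. Even so, a pooled construct needs nicotine with alcohol represented in its frequency component, and it is not.

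**Conclusion.** The point stands in a limited form and is worth acting on before launch. Three things follow directly from the text: there is no frequency measure of nicotine with alcohol; the pooled yes/no item cannot isolate it; and the filter does not match the question it controls. A fourth is an omission: neither the score for skipped items nor the rule for combining the two items is given.

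The selection problem is conditional. It arises at T2 and T3 only if skips are treated as missing or excluded. In that case the comparison is among users only, can be biased in either direction, and at assumed shares of 5% to 20% has power of 0.12 to 0.39 at 5% of variance. With skips scored as zero and all 280 teens included, power at the same share of variance is 0.97. The power figures rest on two-sided 0.05, a simple two-group comparison and the assumed shares. The sign reversal is an illustration, not a prediction.

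**What to change.** 1. Ask two parallel frequency items: alcohol with marijuana, and alcohol with nicotine.
2. Skip each item only when the teen reports no use of one of the two substances it concerns, over the same recall window. Section 4.3 now uses six months for marijuana and nicotine and one month for the peak occasion, so the windows need aligning.
3. Score those logical skips as 0, so that all responding randomized teens enter the H2 analysis. Keep true non-response separate and handle it under the missing-data plan.
4. Split the peak-occasion question into one for marijuana and one for nicotine.
5. State in the analysis section how the items form the combined-use outcome, or that each is analysed separately under the planned multiplicity control.

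The cost is one or two extra survey items and revised skip logic before launch, with slight added burden for teens. Sample size and visits do not change.

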**H4:** Parents in the PN condition will discuss alcohol use and consequences and combining alcohol with other substances more than controls (tertiary outcome).

**H5:** Parent communication will in turn influence student factors (e.g., reduced motives and behavioral willingness; tertiary outcome).

**Summary of Significance.** In summary, the proposed PN intervention is significant because it uses state-of-the-art technology to adapt a novel, evidence-based universal prevention strategy in a flexible, digital format in an underutilized population to address a serious public health concern (alcohol use) among a late adolescent age group whose use is accelerating. It extends the scope of parent interventions by including non-college-bound youth whose career vector includes jobs or military as well as college-bound youth. The digital format provides a more contemporary delivery mechanism that fits the online world and facilitates personalized and customized content. The PN addresses alcohol use and alcohol combined with other substances in an at-risk target population (i.e., high school youth), through an evidence-based approach that is adapted for a broader audience (parents of all high school students) and utilizes technology to effectively implement prevention.

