**PN Program Analytics.**

Program analytics (i.e., log data) to be collected include

total time spent accessing PN, time spent on each module and activities within modules, and number of activities and modules completed. These data will be captured through HTML5 programming and downloaded into Excel. From this data, we will be able to examine the depth of parents’ immersion in the program and distinguish between users who quickly moved through the program versus those with a deeper level of engagement as well as assess accuracy and use them to assess effects of program exposure (i.e., dose).

**Fidelity of PN Use.** We will assess fidelity in several ways. First, we will use the program analytics described above to verify access to PN. Second, we will use practices to ensure that all parents carefully read the PN at least once. We will ask parents to rate each section of the PN in terms of how readable, useful, and interesting they were. Past studies on the Parent Handbook have shown that ratings tend to be uniformly positive, with means on 4-point scales ranging from 3.07 to 3.71 (SDs ranged from .55 to .94). Third, parents will be asked if they had discussed specific topics covered in the PN using 4-point scales ranging from (1) not at all to (4) a great deal. Past studies on the Parent Handbook have shown >70% of parents report they had discussed all topics. In our past studies, we have asked parents to underline segments of the Parent Handbook that resonate for them and make comments in the margins of the materials, and found that >70% return the materials with markings and comments throughout (almost all comments being uniformly positive). In the current study, we will have an option where parents can click on an icon to add a comment on any section of the PN modules. We will encourage them to do so, letting them know that it will help us understand content they particularly like or feel needs to be refined. Based on our previous work, we anticipate >70% of the parents will read the PN thoroughly, rate the content positively, and communicate the content with their teens.

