#### *Intervention Materials and Follow-Up Surveys:*

At the 1-month follow-up to the baseline survey teens in both treatment and control conditions which will be surveyed to allow us to examine any changes in proposed mediator variables. After the baseline, dyads will be randomized to the treatment and active control conditions. Parent respondents will receive either PN or the active control (SAMHSA website) link. Parents in both conditions will be instructed to read the materials and discuss the information with their teens during the next month. Both conditions will take the same length of time to navigate, and identical fidelity questions and prompts will be used. Instructions for how to register and use the site will be provided on the home page. Parents who do not register with the website will receive reminders every 5 days for three weeks; after three weeks, study staff will contact parents by telephone and encourage them to register. Implementation of technology interventions can be challenging due to participants forgetting, fatiguing, or believing they have learned all they need. The GfK staff will send periodic reminders to parents to use the website; RP staff will be available to provide technical assistance if parents have problems using the website. In our previous studies, we have had parental compliance rates with e-surveys, hard-copy Parent Handbook, parent-ratings of the Parent Handbook and so on that have reliably exceeded 88%. We anticipate no problems regarding use of the web-PN.

Following the intervention dissemination, teens and parents will be asked to complete an immediate posttest survey (1-month) and teens will complete a second posttest at 6-months following the same procedures as detailed above.

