Other	Alcohol Motives (tertiary/other outcome)	Project years 1-2	Using the past six months as a time reference, participants will be asked about their motivations to use alcohol. Twenty items for each substance will assess motives for using alcohol, such as ?to be sociable? and ?to forget about your problems? on a 5-point scale ranging from (1) almost never/never to (5) almost always/always.
Other	Alcohol Expectancies (tertiary/other outcome)	Project years 1-2	Alcohol expectancies will be measured using a 7-point scale ranging from (-3) strongly disagree to (3) strongly agree. Items will assess how likely a variety of alcohol-related consequences will be experienced in the next few months. For example, items, be worded specifically for alcohol use, such as ?I will feel badly about myself because of my drinking.?
Other	Alcohol Willingness (tertiary/other outcome)	Project years 1-2	Response options for willingness items will be on a 7-point scale ranging from (1) strongly disagree to (7) strongly agree. Willingness to use alcohol will be measured to assess participants? willingness to 1) drink once or twice in two hours; 2) drink 3-4 times in two hours; and 3) drink 5+ times in two hours. Willingness to use marijuana and COMBINE will be assessed individually with four items asking their willingness to use marijuana/ COMBINE occasionally, regularly, weekly, and daily.
Other	Alcohol Norms (tertiary/other outcome)	Project years 1-2	Perceived norms of drinking for the past six months will be measured using the DDQ using closest friend as a referent. To assess peer injunctive norms of alcohol use participants will be asked to indicate how acceptable their closest friends would find of a list of situations (e.g., drinking enough alcohol to pass out) using a (1) strongly disapprove to (7) strongly approve scale.
Other	Parental Communication (other/tertiary outcome)	Project years 1-2	Parental communication about alcohol, nicotine, and marijuana use, COMBINE, and alcohol consequences will be assessed separately for parent and teen. Participants will be asked whether their parent discussed these topics (yes/no) with them within the past six months. Items include topics such as ?the importance of not being pressured to drink to fit it? and ?how marijuana works in the body?.

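### Parental communication, the H4 outcome and an Aim 2 mediator, is scored yes/no per topic over six months although a 4-point amount scale is already planned for parents; if control yes rates are high, this costs power

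*Combined protocol and SAP*

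**What the plan says.** H4 (Significance, Aim 2) reads: "Parents in the PN condition will discuss alcohol use and consequences and combining alcohol with other substances more than controls". It is a tertiary outcome.

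The Parental Communication row of section 4.3 says the construct "will be assessed separately for parent and teen", and gives the response format: "Participants will be asked whether their parent discussed these topics (yes/no) with them within the past six months". Table 2 lists parent communication as a mediator reported by parent and teen at T2, the 1-month survey.

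Under Participant Recruitment and Procedures: "Parents in both conditions will be instructed to access the materials and discuss the information with their teens during the next month". So controls are also asked to hold these conversations.

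Under Fidelity of PN Use, parents will be asked whether they had "discussed specific topics covered in the PN using 4-point scales ranging from (1) not at all to (4) a great deal". The Protection of Human Subjects section (Intervention Materials and Follow-Up Surveys) adds, of the two conditions, that "identical fidelity questions and prompts will be used". The graded item therefore appears to be asked in both arms.

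The fidelity paragraph reports that more than 70% of parents in past Parent Handbook studies said they had discussed all topics. The documents give no control-arm rate, no teen-reported rate, no rule for combining topics into a score, and no power figure for H4.

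**The concern.** H4 is about more discussion. A yes/no item gives the same answer for a passing mention and a long conversation. If most control parents have mentioned most topics, a PN effect on depth will largely go unrecorded.

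Three features of the plan make high yes rates plausible, at least for parent report. Controls are instructed to talk. Most earlier Handbook parents reported covering every topic. And the recall window is six months while the mediator is taken at 1 month, so about 6 − 1 = 5 months of talk before baseline also count as yes in either arm.

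At stake are H4 itself and the Aim 2 paths that run through communication. The plan tests mediation by joint significance, so the group-to-communication path must itself reach significance. Power lost there limits every indirect effect through communication.

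**Working it through.** **1. The plan's own figures.** Section 4.4 (Statistical Design and Power) has no figure for H4. Its Aim 2 figures reproduce:
- Regression, 5% unique variance, R² = 0.25, power 0.80: f² = 0.05/0.75 = 0.0667; n = 7.85/0.0667 + k + 1 = 124 for 5 predictors and 125 for 6. Stated: about 125.
- Logistic, event rate 0.20, multiple correlation 0.30: n = 7.85 / [0.20 × 0.80 × (ln OR)² × (1 − 0.30²)] gives 173 for OR 1.75 and 113 for OR 2.00. Stated: about 170 and 110.

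Neither calculation concerns the effect of group on communication.

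**2. Inputs.**
- From the documents: 1:1 allocation and 320 dyads expected at 1 month, so 320/2 = 160 per arm.
- Assumed: two-sided alpha 0.05, 10 topics, inter-item correlation 0.4, person-level PN shift 0.3 SD, and control yes rates per topic from 50% to 95%.

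**3. Model.** Each topic has a latent normal amount with unit variance: √0.4 × person effect + √0.6 × topic effect. PN moves the person effect by 0.3 SD, which is 0.3 × √0.4 = 0.19 SD per topic. Yes means above the first cut-point, which is set by the control yes rate. The yes group is split into equal thirds for the three upper levels. The yes count and the 4-point mean are each compared by t test in simulated trials.

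**4. Results for a 10-topic score.**

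| Control yes rate per topic | Yes/no count | 4-point mean | Loss (points) |
|---|---|---|---|
| 50% | 0.66 | 0.68 | 2 |
| 70% | 0.61 | 0.69 | 8 |
| 80% | 0.55 | 0.69 | 14 |
| 90% | 0.45 | 0.67 | 22 |
| 95% | 0.36 | 0.69 | 33 |

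A repeat with a different seed stayed within 0.02 of each figure, so the small differences within the 4-point column are simulation noise.

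**5. Plausibility check.** The SD of the latent 10-topic mean is √(0.4 + 0.6/10) = 0.678, so the shift on it is 0.19/0.678 = 0.28 SD. With 160 per arm the noncentrality is 0.28 × √80 = 2.50, giving power of about 0.70 for an error-free mean. The 4-point score comes close to this at every yes rate; the yes/no count does not.

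**6. Single topic.** Because no combining rule is stated, one topic alone was also checked, with a 0.30 SD shift on that topic and 160 per arm. Power for yes/no against 4-point is 0.57 vs 0.67 at 50% yes, 0.50 vs 0.70 at 70%, 0.43 vs 0.70 at 80%, 0.30 vs 0.70 at 90% and 0.20 vs 0.69 at 95%. The yes/no item needs 1.3, 1.6, 2.0, 3.0 and 4.7 times the sample, respectively.

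**7. Which row applies?** If more than 70% of parents discuss all topics, every topic is at least 70% yes. With 10 topics and correlation 0.4, a 95% rate per topic gives about 72% answering yes to all. This places a group that behaves like the earlier Handbook parents near the bottom row. It does not place controls or teens there.

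**The case against.** The strongest reply is that the ceiling is inferred. The only discussion rate is parent report from people who received the Handbook, so it is a treated-group rate, while the quoted section 4.3 item is worded for the teen. The topic list also covers nicotine, marijuana and combined use, which the plan describes as added content, with a module on other drugs that is optional. Rates for these may be much lower. All of this stands: a reader might infer that the yes/no score sits at its ceiling in controls, and the documents do not support that. At 50% yes the loss is about 2 points.

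A reader might also compute a more dramatic contrast, such as 0.67 vs 0.96 at 95% yes. That comes from shifting every topic by 0.3 SD, which is 0.3/0.678 = 0.44 SD on the 10-topic mean. A 0.3 SD difference between two groups of 160 has power of only about 0.76 even when measured without error.

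A count of topics is also a fair measure of breadth, and breadth is one reading of H4, so yes/no is not invalid. Parents will apparently give graded answers anyway, and the Data Analysis section plans factor analyses to guide how indices are combined. This makes the change cheaper, but section 4.3 still names yes/no as the format for the communication outcome, and combining indices does not alter the response options.

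Finally, the six-month window would dilute a graded item too. That is correct, and the fix therefore covers the window.

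**Conclusion.** The point holds as a conditional one. The plan tests a hypothesis about more discussion with a yes/no item, in a trial where both arms are told to talk, while a graded item is already planned for parents. The yes/no score had lower power at every control rate examined. For a 10-topic score the loss runs from about 2 points at 50% yes to 22 at 90% and 33 at 95%. High rates are plausible for parent report and unknown for controls and teens.

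The size rests on the assumed topic count, correlation, effect size, category split and control rate, none of which the documents give. Even the 4-point mean reaches only about 0.67 to 0.69 under these assumptions, so the change recovers lost power but does not make H4 well powered. The outcome is tertiary, and the primary comparison on alcohol use is unaffected. The change is still worth making before the surveys are fielded.

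**What to change.** In section 4.3:
- Name the mean of the 4-point amount items, over the section 4.3 topic list, as the H4 outcome and the communication mediator in both arms.
- For parents, use the scale already planned under Fidelity of PN Use, and state explicitly that controls answer the same items. For teens, replace the yes/no response options with the same four points.
- At the 1-month survey, ask about the period since baseline instead of the past six months.
- Keep yes/no (score above 1) as a derived descriptive count of breadth.

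Cost: new response options for teens, and for parents an alignment of the fidelity topics with the section 4.3 list. Results will be somewhat less comparable with earlier yes/no data, and the reliability figure that Table 2 gives for the cited measures (above .75) may not carry over, so alpha should be re-estimated, as the Data Analysis section already plans for multi-item measures.
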